### 3.2g. Data Analysis

1. The feasibility of the program will be evaluated by assessment of recruitment, retention, and participant evaluation. Itemized logs of recruitment sites, methods, responses, eligible subjects, and consented subjects will be documented. Retention will be evaluated through documentation of weekly attendance and compliance with RT-CGM site changes. As part of the feasibility assessment, we will also track the number of RT-CGM sensor failures, RT-CGM placement sites, time to failure, and any adverse sensor site problems. Acceptability will be determined through participant evaluation (Appendix C).

2.) We will calculate means and standard deviations of within-group and between-group differences from baseline to program completion (8th week) and post-program (12th week) on the outcomes of FOH, self-management, glycemic control (A1C), and GV.

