
#### 2. RESEARCH PLAN

##### B. Specific Aims

**The specific aims of this IRSP pilot study are:**

1. Determine the feasibility of the 8-week fear reduction intervention FREE in young adults with T1DM who report FOH. Feasibility will be determined through analysis of recruitment, retention, and participant evaluation.
2. Obtain means and standard deviations of within-group and between-group differences from baseline to program completion (8th week) and post-program (12th week) on the outcomes of FOH, self-management, glycemic control (A1C), and GV. This data will be used for calculation of effect sizes for a future larger study.

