### 3.2. Design and Methods

**3.2a. Overview.** Following a 1-week run-in phase, ten young adults aged 18 to 30 years with T1DM ( $\geq 1$  year) and who experience FOH will be randomized to an intervention or attention control group. The intervention group will participate in eight weekly one-hour sessions using a CBT-based approach (FREE), wear a RT-CGM device, and keep a daily diary. The attention control group will also wear a RT-CGM device for 8 weeks but will not participate in weekly sessions and will not keep a diary. Data will be collected: (1) at the beginning of a 1-week run-in period (week 0); (2) at completion of the intervention at the end of 8 weeks (week 8); and (3) post-program at 12 weeks. At completion, FOH, self-management, and A1C will be measured and RT-CGM recordings will be analyzed to determine within-group and between-group differences.

**3.2b. Setting and Sample.** The study intervention will take place at the University of Illinois at Chicago (UIC) Medical Center and College of Nursing. Inclusion criteria: (1) 18-30 years old, (2) diagnosed with T1DM  $\geq 1$  year and receive medical care from an endocrinologist, (3) use insulin pump therapy, and (4) have self-reported FOH (screening questionnaire). Exclusionary criteria: (1) pregnant or breastfeeding, (2) actively treated for a mental health condition, (3) have a co-existing chronic illness or taking medications (excluding insulin) that may influence diabetes self-management or GV.

**3.2c. Recruitment.** Subjects will be recruited through Chicago metropolitan area university medical centers, local diabetes websites, and organizations using flyers, e-announcements, and recruitment letters. At UIC, we will identify potentially eligible subjects through the electronic medical record system and send recruitment letters. The University of Illinois clinics saw over 900 patients with T1DM; thus, there is a sufficient pool from which to recruit. We have been successful in recruiting using these methods for our previous studies.

**3.2d. Sample Size Determination.** The sample size of 10 subjects ( $n = 5$  intervention group; 5 intention control group) will be sufficient to test the feasibility of the study protocol and to obtain preliminary outcome measures.

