**3.2e3. Subject Retention Strategy.** Both the FREE intervention group and the attention control group will (1) wear a RT-CGM; (3) receive reminders of their next appointment; and (4) have weekly visits to change the RT-CGM site. The weekly appointment reminders and RT-CGM site changes will be used to facilitate subject retention. Those in the FREE group will (5) receive additional intervention sessions week 1-8 and (6) weekly CGM downloads with GV analysis when they attend each session. (7) All subjects will be compensated for their time.

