### 3.2f. Measures.

**3.2f1. Baseline and Post-Intervention Measures.** *Self-report instruments* will be used to obtain demographic and health information, previous history of hypoglycemia, fear of hypoglycemia, self-management behaviors, and related variables (self-efficacy, anxiety, diabetes distress). The scales have strong psychometric properties and have been validated in T1DM populations (Table 1). *Glycemic control* will be measured with a fingerstick for A1C for assessment of longer-term glycemic control using A1C Now® (Chek Diagnostics, Indianapolis, IA).

**3.2f2. Ongoing Measures: Diary.** A daily diary will be used to measure daily fear levels and perceptions of GV for FREE participants only.

Table 1. Measures		
Variables	Measure	Frequency
Aim 1 Feasibility		
Recruitment Retention Acceptability	Number of eligible respondents/Number consented Attendance rate; Completion rate Participant evaluation (Appendix C)	Ongoing Weekly Week 8
Aim 2 Program outcomes		
Previous hypoglycemia	Hypoglycemia Patient Questionnaire 	Week 0
FOH	Hypoglycemia Fear Scale (HFS-2  ) FREE group only: Daily FOH Diary: Fear level  (Appendix B)	Week 0, Week 8, 12 Daily
Glycemic measures Glycemic control Glycemic variability	A1C (A1C Now®) RT-CGM (Dexcom®): Daily glucose standard deviation (GlucSD), continuous net glycemic action (CONGA), coefficient of variation (CV%), interquartile range (IQR) and mean amplitude of glycemic excursions (MAGE) (see 3.2f3) FREE group only: Daily FOH diary: GV perception  (Appendix B)	Week 0, Week 8, 12 Daily
Perception of glycemic variability		Daily
Diabetes self-management	Diabetes Self-Management Questionnaire 	Week 0, Week 8, 12
Other psychological covariates to characterize sample: self-efficacy, anxiety; mood, diabetes distress	Self-Efficacy for Diabetes  PROMIS Anxiety and Depressive Mood Scales Diabetes Distress 	Week 0, Week 8, 12 Week 0, Week 8, 12 Week 0, Week 8, 12

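### Acceptability rests on one participant evaluation at week 8, with no stated way to collect the views of subjects who leave earlier

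*Combined protocol and SAP*

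**What the plan says.** Aim 1 (section B, Specific Aims) rests on three components: "Feasibility will be determined through analysis of recruitment, retention, and participant evaluation". Section 3.2g, item 1, then says where the acceptability result comes from: "Acceptability will be determined through participant evaluation (Appendix C". No other source is named.

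Table 1 (section 3.2f) lists three Aim 1 variables: recruitment, retention and acceptability. For the last two the measures read "Attendance rate; Completion rate Participant evaluation (Appendix C", and the frequencies for the three read "Ongoing Weekly Week 8". Taken in order, recruitment is tracked throughout, retention every week, and acceptability once, at week 8.

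On subjects who might leave, the retention strategy (3.2e3) relies on reminders, visits and payment: "The weekly appointment reminders and RT-CGM site changes will be used to facilitate subject retention". Section 3.2g adds: "Retention will be evaluated through documentation of weekly attendance and compliance with RT-CGM site changes". Neither place mentions an evaluation at exit or a record of the reason for leaving. Section 3.2j says the study's purpose is to inform a larger one, and names acceptability among the things it should inform.

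**The concern.** A form given only at week 8 reaches only people who are still there. Those who stop early may have found the program less acceptable than those who stay. That is an inference, since the documents give no data on it, but it is plausible: section 3.2e1 asks FREE subjects for eight weekly sessions, homework, a daily diary and graded approach to situations they fear. If the inference is right, the error runs in one direction, and the reported figure looks better than it should.

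Attendance logs will show that a subject left. They will not show what the subject thought of the program or why they stopped. Those designing the larger trial would therefore lack the information most useful for changing the program. Views not collected at exit may be lost for good.

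**Working it through.** **Inputs from the documents**
- Source of the acceptability result: participant evaluation only (3.2g, item 1).
- Timing: week 8, once (Table 1). The rows are run together in the extracted text, but three variables against three frequencies leave one natural reading.
- Size: 5 per arm (3.2d, "intervention group; 5 intention control group"), so 5 + 5 = 10, which agrees with the timeline in 3.2h (4 + 4 + 2 = 10).
- Expected dropout: none stated. The plan has no figure of its own to reproduce.

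**Assumptions:** a yes/no item (the form was not seen), independent losses, and dropout rates chosen to show a range.

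**Can other planned data stand in for a leaver's evaluation?**

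| Planned data | What it records | Leaver's opinion or reason? |
|---|---|---|
| Attendance, completion, site-change compliance (Table 1, 3.2g) | That and when a subject stopped | No |
| Sensor failures and site problems (3.2g) | Device performance | No |
| Daily diary (3.2f2) | "A daily diary will be used to measure daily fear levels and perceptions of GV for FREE participants only" | No, and none for controls |
| Session audiotapes (3.2e1) | Fidelity to the manual, FREE arm only | Chance remarks at most |

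The documents do not say whether controls also receive the evaluation. FREE-only items in Table 1 are marked as such and this one is not, so both cases are shown below.

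**Effect of missing forms**

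With n randomized and k forms missing, k/n of the proportion is undetermined:
- One arm of 5: 1/5 = 20 points for one missing form, 2/5 = 40 points for two.
- All 10, if both arms get the form: 1/10 = 10 points per missing form.

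If everyone who responds is favourable, the report shows 100%. If every leaver was unfavourable, the figure for all randomized is (n − k)/n:
- One leaver in an arm of 5: 4/4 = 100% reported, against 4/5 = 80%.
- Two leavers: 3/3 = 100% reported, against 3/5 = 60%.

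**Sampling uncertainty, for scale**

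Exact (Clopper-Pearson) 95% intervals:
- 5/5: 48% to 100%
- 4/4: 40% to 100%
- 3/3: 29% to 100%
- 4/5: 28% to 99.5%
- 3/5: 15% to 95%

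These are wide, but they describe sampling error only. They make no allowance for who is missing.

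**How likely is at least one missing form?**

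P(at least one) = 1 − (1 − d)^n, where d is the early dropout rate. For example, at d = 20% and n = 5 it is 1 − 0.8^5 = 0.672.

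| Assumed dropout d | One arm of 5 | All 10 |
|---|---|---|
| 10% | 41% | 65% |
| 20% | 67% | 89% |
| 30% | 83% | 97% |
| 40% | 92% | 99% |

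The probability passes one half when d exceeds 1 − 0.5^(1/n):
- n = 5: 1 − 0.5^(1/5) = 12.9%
- n = 10: 1 − 0.5^(1/10) = 6.7%

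**The case against.** The strongest reply is that the gap lies exactly where text was not available. Both mentions of the evaluation point to Appendix C, which could contain an instruction for early leavers, and consent pages were also removed. This stands as a limit: the available text does not establish that the full plan lacks an exit route, and the fix is worded accordingly.

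Second, Aim 1 is read as a whole. A favourable result of 4/4 would sit beside a completion rate of 4/5, and a reader could work out the 80% worst case. That is true, provided the two are reported together. The leaver's opinion and reason would still be unknown, and 3.2g sets no denominator for acceptability. The session tapes do not fill the gap either, since they are made for fidelity and exist in one arm only.

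Third, week 8 is a sensible time because it is the first point at which a subject has seen the whole program. This is also right, and it is a reason to keep week 8 for those who reach it. It is no reason to collect nothing from those who do not.

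Fourth, the result is descriptive at this size and the documents tie no decision rule to it. That limits the weight of the point. It does not remove the tilt toward subjects who stay, which the confidence interval does not measure.

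**Conclusion.** The concern holds. As the available text stands, a named component of Aim 1 would be drawn only from subjects still in contact at week 8, and no other planned data would supply the missing views.

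The size is 20 points per missing form in an arm of 5, or 10 points across all 10 subjects if both arms are asked. These figures assume a yes/no item, and the 80% and 60% examples further assume that every leaver was unfavourable. At least one missing form is more likely than not once early dropout passes 12.9% in one arm or 6.7% overall, assuming independent losses. With no early leavers the effect is zero.

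The plan should be changed on this point, though the point does not undermine the pilot. Confidence is moderate because Appendix C was not seen.

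**What to change.** - **Table 1, Acceptability:** change the timing from week 8 to *Week 8, or at withdrawal if earlier*.
- **Section 3.2g, item 1:** record the reason for leaving. Report acceptability by arm, for each arm given the form, with the number randomized, the number responding, and the number responding at withdrawal.
- **If Appendix C already provides for completion at exit:** say so in Table 1 and add only the reporting line.

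The cost is small: one existing form and one log entry at exit, with no change to eligibility, sample size or the intervention. Some leavers will decline, so the bias is reduced but not removed. Forms completed at withdrawal reflect less exposure to the program, which is why they are counted separately. The acceptability result may look less favourable than it otherwise would.

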**3.2e. Procedures.** Study staff will screen subjects for inclusion/exclusion criteria. Scores of 3 or 4, indicating that worry occurs *often* or *very often*, on any item on the worry scale (4-point Likert) of the Hypoglycemia Fear Scale (HFS-2) will be used to determine the presence of FOH (personal communication [name], 5/26/15). Those who meet the study criteria will be scheduled for an appointment at the College of Nursing for the start of the 1-week run-in period to: obtain consent and baseline measures (Table 1, Week 0) and apply a RT-CGM device with instructions provided on its care. Following the 1-week run-in period, subjects will be randomized to the FREE intervention or attention control group. During the study period, subjects will continue to receive their usual diabetes care with their health care provider. The subjects will be encouraged to discuss any questions regarding blood glucose management with their diabetes health care provider.

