**3.2f3.Ongoing Measures: Glycemic Variability.** Subcutaneous interstitial glucose levels will be monitored during the run-in phase (over a period of 7 days) and the 8-week intervention (FREE intervention and attention control groups) using a Dexcom G4 Platinum® (San Diego, CA). A glucose sensor and recorder will be placed on the abdomen and changed weekly by a trained study staff member (a registered nurse). All subjects will be able to view their RT-CGM values. At the end of each week, all data will be downloaded to the Dexcom Software and examined for glycemic trends and excursions. The weekly glucose summary will be provided to subjects in the intervention group at each weekly session to provide feedback on their glucose trends. Those in the attention control group **will be able to view** their CGM readings in real-time but **will not** receive weekly summaries. Rather, at the end of the full study (i.e., 12 weeks), they will receive their weekly

summaries.

To analyze GV for study outcomes, the raw data will be downloaded to an EXCEL spreadsheet. The research staff will be trained on data cleaning, confirmation of regular calibration, identification of errors, and review of missing data or time-points. The amount of time spent in hypo- and hyperglycemia will be calculated (% and minutes; < 70 and > 180 mg/dl). GV will be determined by calculating the daily glucose standard deviation (GlucSD), continuous net glycemic action (CONGA), coefficient of variation (CV%), interquartile range (IQR), and mean amplitude of glycemic excursions (MAGE). These are measures that are recommended to obtain a comprehensive evaluation of GV.

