### 3.2h. Timeline

Year 1	Mar	Apr	May	June	July	Aug	Sept	Oct	Nov	Dec	Jan	Feb	Mar	Total
Study set up	X	X	X											
FREE subjects				2		2			1					5
Control subjects				2		2			1					5
Total subjects				4		4			2					10

**3.2j. Pilot study limitations.** One of the limitations is that the small convenience sample may not be representative of the population. This limitation is offset by the fact that this is strictly a feasibility pilot to inform and strengthen a larger study in terms of recruitment, retention and acceptability.

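### Should the pilot report visit-level values and baseline-adjusted differences rather than only means and SDs of change?

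*Combined protocol and SAP*

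**What the plan says.** Aim 2 (section B, Specific Aims) is to "Obtain means and standard deviations of within-group and between-group differences from baseline to program completion" and to post-program at week 12, for fear of hypoglycemia, self-management, A1C and glycemic variability. It adds the purpose: "This data will be used for calculation of effect sizes for a future larger study". Item 2 of 3.2g repeats the aim almost word for word: "We will calculate means and standard deviations of within-group and between-group differences from baseline to program completion".

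The values behind these changes are collected. Table 1 in section 3.2f schedules the fear scale, A1C and the self-management questionnaire at weeks 0, 8 and 12. Section 3.2f3 has glucose recorded through the run-in week and the 8-week program. Baseline is measured before allocation; section 3.2e states: "Following the 1-week run-in period, subjects will be randomized to the FREE intervention or attention control group".

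The claims are limited. Section 3.2d says that 10 participants, 5 per arm, "will be sufficient to test the feasibility of the study protocol and to obtain preliminary outcome measures". Section 3.2j says that "this is strictly a feasibility pilot to inform and strengthen a larger study in terms of recruitment, retention and acceptability". The documents do not say how the larger study will be analysed.

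**The concern.** There are two reasons to hesitate over item 2.

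First, with 5 per arm, randomization can leave the arms well apart at baseline. Unless baseline and follow-up correlate perfectly, the arm that starts higher will tend to fall further, so in any one pilot the difference in change partly reflects the starting gap. A table of changes does not show that gap.

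Second, the pilot is meant to feed the planning of a larger trial. If that trial adjusted for baseline by ANCOVA, its sample size would depend on the residual SD after adjustment. That in turn depends on the visit SDs and the baseline to follow-up correlation, none of which can be recovered from the SD of change alone. The larger trial could then be planned at the wrong size.

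**Working it through.** **Inputs.** From the documents: 5 per arm (3.2d; the timeline in 3.2h agrees, 2 + 2 + 1 = 5 in each arm). There is no power calculation to reproduce. The documents give no correlation ρ and no visit SDs, so these are assumptions: ρ from 0.3 to 0.8, and k = follow-up SD / baseline SD from 0.8 to 1.25, with baseline SD set to 1. Data are taken as normal and complete.

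**Step 1: chance imbalance.** SD of the baseline mean difference = √(1/5 + 1/5) = √0.4 = 0.63 outcome SDs. The chance of a gap of at least 0.5 SD is about 43%, and of at least 1 SD about 11%. With equal visit SDs, a gap of g shifts the expected difference in change by −(1 − ρ)g. For a gap of 0.63 the size is 0.5 × 0.63 = 0.32 SD at ρ = 0.5 and 0.3 × 0.63 = 0.19 SD at ρ = 0.7. The gap is equally likely in either direction, so the shift averages to zero over randomizations. In 200,000 simulated pilots with no treatment effect, the mean difference in change was 0.00 at every ρ.

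**Step 2: what a wrong planning SD would cost.**
- Variance of change = 1 + k² − 2ρk.
- ANCOVA residual variance = k²(1 − ρ²).
- The first minus the second = (1 − ρk)², which is never negative. Sizing an ANCOVA trial on the SD of change can therefore overstate N but not understate it, apart from the one degree of freedom spent on the slope.

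For k = 1 the ratio is 2(1 − ρ)/(1 − ρ²) = 2/(1 + ρ):

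| ρ | N overstated by | n per arm, ANCOVA | n per arm, change score |
|---|---|---|---|
| 0.3 | 2/1.3 = 1.54 | 41 | 63 |
| 0.5 | 2/1.5 = 1.33 | 48 | 63 |
| 0.7 | 2/1.7 = 1.18 | 54 | 63 |

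The n columns assume an effect of 0.5 SD of change, two-sided 5% and 80% power, purely as illustration. Over the full assumed range of k and ρ the factor runs from 1.00 (k = 1.25, ρ = 0.8) to 1.99 (k = 0.8, ρ = 0.3).

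**Step 3: what 10 participants can tell about these inputs.** A pooled SD on 8 degrees of freedom has a 95% CI of 0.675 to 1.916 times its estimate. N for a fixed effect scales with the square: 0.675² = 0.46 to 1.916² = 3.67. A pooled within-arm correlation of 0.5 has a Fisher 95% CI of tanh(0.549 ± 1.96/√6) = −0.25 to 0.87. Put through 2/(1 + ρ), that interval gives 2/0.75 = 2.67 to 2/1.87 = 1.07, which is wider than the whole span from 1.18 to 1.54. The correlation from this pilot could not tell the scenarios apart.

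**Step 4: what adjustment within the pilot would add.** Results are from simulation with k = 1, 5 per arm and no effect:

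| ρ | Mean 95% CI width, adjusted | Mean 95% CI width, change | Adjusted CI wider in |
|---|---|---|---|
| 0.3 | 2.95 | 3.35 | 34% of pilots |
| 0.5 | 2.68 | 2.83 | 46% |
| 0.7 | 2.21 | 2.19 | 60% |
| 0.8 | 1.86 | 1.79 | 67% |

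At ρ = 0.5 the fitted slope ranges from −0.20 to 1.20 (95% range), and the adjusted estimate lies farther from the truth than the change-score estimate in 44% of pilots.

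**Step 5: aim against analysis.** Aim 2 calls for means and SDs of differences from baseline at weeks 8 and 12, for later effect sizes. Item 2 computes those quantities for the same outcomes at the same times. If the larger trial analyses change, the SD of change is the right planning input.

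**The case for a change.** The best case for acting is that the addition is cheap and informative. Means and SDs by visit would let a reader see the imbalance that occurred. Together with the SD of change they also yield the correlation, because SD²(change) = SD₀² + SD₁² − 2ρ·SD₀·SD₁. The point has some force for the fear scale: section 3.2e admits participants on high worry items of the scale that also serves as the outcome, so baseline and follow-up SDs may well differ.

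Part of this stands. Section 3.2g does not name a table by visit, and one would be good reporting. But each change is formed from a baseline and a follow-up value, so both are already in the data set. A short feasibility protocol need not list every descriptive column, and its silence does not rule that table out. Entry on a high worry score affects both arms alike because allocation comes later, so on average it does not bias the between-group difference.

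The further requests, for correlations and adjusted differences, are weaker. Three measures at two follow-ups make 3 × 2 = 6, and five glycemic variability indices at week 8 bring the total to at least 11 of each from 10 people. The adjusted figures would have to be labelled descriptive, with a warning not to size a trial on them alone.

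**Conclusion.** The concern does not hold. The planned analysis matches Aim 2, the change-score comparison is valid under randomization, and the modest claims in 3.2d and 3.2j do not depend on baseline adjustment. The possible harm requires a larger trial analysed by ANCOVA, which no section mentions. Even then it is a conservative error of 1.18 to 1.54 in N at assumed correlations of 0.7 to 0.3 with equal SDs (1.0 to 2.0 over the wider assumed range). That is well inside the 0.46 to 3.67 uncertainty that N = 10 brings in any case. Adjustment in the pilot would narrow the interval slightly at low correlation and widen it at 0.7 and above. Means and SDs by visit are a sensible routine table, but omitting to name them is a matter of reporting detail and changes no result. The figures assume normal, complete data; the correlations and SD ratios are illustrative because the documents give none.
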